#### Clinical Visit around 21 days post-tenotomy (This visit is part of subject's routine care)

The subject will be assessed for complications. The treating physician will provide a Dimeglio score. A parental survey will be administered regarding quality of care, postoperative care, and perception of subject's pain level.

REDCap Survey questions to be sent to parents post TAL						
REDCap Survey	1. On a scale of 1-5, with 1 being no pain and 5 being extreme					
Postop Day 1	pain, how much pain is your child having today due to the					
	procedure?					
	2. On a scale of 1 to 5, with 1 being no irritability and 5 being					
	extreme irritability, how irritable is your child today due to the procedure?					
	3. How many doses of Tylenol (acetaminophen) has your child					
	been given today due to pain from the procedure?					
	4. If applicable, please list any other problems that your child is					
	having today, due to the procedure.					
REDCap Survey	1. On a scale of 1-5, with 1 being no pain and 5 being extreme					
Postop Day 7, 14	pain, how much pain has your child had over the last week due to					
& 21	the procedure?					
	2. On a scale of 1 to 5, with 1 being no irritability and 5 being					
	extreme irritability, how irritable has your child been over the last					
	week due to the procedure?					
	3. On average, how many doses of Tylenol (acetaminophen) per					
	day have been given to your child over the last week due to pain					
	experienced from procedure?					
	4. If applicable, please list any other problems your child has had					
	over the last week, due to the procedure.					

# **Routine Care**

All research activities will be conducted during routine care visits. The subject will not be asked to attend any research-only visits. Serial casting and the tenotomy procedure are routine care.

# Standardizing the Environment

The environment the subject experiences during their weekly casting visits, the day of the tenotomy, and POD 21 will be standardized to ensure observed behaviors are due to the procedures taking place and not related to new stimuli. To standardize the environment the following will occur:

- CCLS will be present
- Casting by Moonlight (Turning off bright overhead lights, turning on small indirect light)
- Developmentally appropriate coping strategies, such as oral sucrose, music, soothing touch, and Tranquilo Vibration Mat, will be implemented upon CCLS, family, and or healthcare staff's discretion. The study is not limited to the following examples of coping strategies.

Study procedures	Enrollment Visit	Weekly Casting Visits	Final Casting Visit (1 week prior to tenotomy)	Day of Tenotomy	POD1	POD7	POD14	POD 21
Informed Consent	Х							
Demographics	Х							
Dimeglio Score	Х			X (Prior to tenotomy)				Х
FLACC Scale		Х	Х	Х				
HR and O2 Levels via Pulse Ox		Х	Х	Х				
CCLS Assessment of		Х	Х					
Temperament								
Randomization			Х					
Parental Assessment of			Х					
Temperament								
Application of J-Tip and				Х				
L.M.X.4 Cream based on								
randomization assignment								
Parental REDCap Survey					Х	Х	Х	Х

# Schedule of Events

Adverse Event/Complication		Х		Х
Review				

#### 7.0 Risks

#### L.M.X.4 (4% Lidocaine) Topical Anesthetic Cream Risk

L.M.X.4 cream, is a topical anesthetic cream that may cause rash, redness, irritation, or swelling at the site of application. There is a risk that this drug may cause problems with heart rhythm.

#### J-Tip with 1% Xylocaine MPF Risks

Xylocaine may cause rash, redness, irritation, or swelling. There is a risk that this drug may cause problems with heart rhythm.

#### Breach of Confidentiality Risk:

During this study every attempt will be made to keep the patient's protected health information (PHI) private. Most study data will be maintained in a Vanderbilt REDCap database. Vanderbilt Redcap is a secure, web-based application for building and managing online databases. The data obtained and stored in Redcap will only be accessible by research personnel. Participating site, Texas Scottish Rite Hospital for Children, will be provided with access to the Vanderbilt REDCap database. The participating site will be able to view their records in the database but will not be able to view Vanderbilt's records. Any data sent to non-key study personnel for statistical analysis will be de-identified (dates will be shifted using a Redcap feature). Any physical study forms (ex. consent documents, surveys) will be kept in a locked cabinet in the principal investigator's office]. All study data will be maintained for 6 years following study completion. Following this 6 year period, the Redcap database will be archived and all physical study forms will be disposed of in shred-it confidentiality bins provided by VUMC.

#### Benefits

If it is determined that the utilization of the J-Tip system is equal to or more effective at reducing pain in infants undergoing a tenotomy than L.M.X.4 cream is, the potential benefits of this study may include better pain management in infants undergoing a tenotomy in the future. In addition, a reduction in the amount of time required to anesthetize the surgical area from 30 minutes with L.M.X.4 cream to 1-2 minutes with a J-Tip injection would decrease the overall length of the visit and cost of procedure, thus increasing quality, safety, and value.

#### 8.0 Reporting of Adverse Events or Unanticipated Problems involving Risk to Participants or Others

The relationship of each adverse event to treatment rendered as judged by the investigator will be recorded on the Adverse Event Report Form. Due to the nature of the procedure involved in this study, certain adverse events may be considered normal sequalae associated with the procedure and will only be recorded if additional treatment is required or considered to be clinically significant. See specific indications for expected adverse events/complications due to nature of diagnosis.

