# 2.0 Hypothesis and Specific Aims

Aim 1: Determine which pain management method, L.M.X.4 Cream vs. J-tip 1% Xylocaine MPF Injection, provides the greatest pain relief to infants with clubfoot undergoing an inoffice percutaneous TAL. Hypothesis: J-tip 1% Xylocaine MPF injection will provide equal or greater pain control when compared to L.M.X.4 cream in infants undergoing an in-office percutaneous TAL.

Aim 2: Determine if there is a difference in the rate of adverse events between the two pain management methods, L.M.X.4 Cream vs. J-tip 1% Xylocaine MPF Injection. Hypothesis: J-tip 1% Xylocaine MPF injection will not be associated with an increased rate of adverse events in comparison to L.M.X.4 cream in infants undergoing an in-office percutaneous TAL.

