# Tenotomy

On the day of the subject's tenotomy they will receive pain control based on their group assignment- L.M.X.4 cream (with J-Tip Saline) or J-Tip with 0.25mL of 1% Xylocaine MPF (with placebo cream). The treating physician will provide a Dimeglio score. The following procedures will take place:

- Baseline: FLACC and pulse ox data will be recorded as baby is positioned on treatment table
- Application of randomized topical cream (either L.M.X.4 or placebo cream) for 30 minutes timed.
- Peak FLACC and pulse ox data will be recorded within 5 seconds of application of LMX 4 or Placebo Cream
- Consent for tenotomy procedure will be obtained (routine care).
- Baseline #2: FLACC and pulse ox data will be recorded 30 minutes after cream application
- Parents will leave room (routine care).
- Patient stays with healthcare staff (Physician, nurse, CCLS, cast tech, trained research assistant)
- Cream will be removed from the subject's foot (routine care). Peak FLACC and Pulse Ox will be recorded within 5 seconds after cream removal.
- Baseline #3: FLACC and pulse ox data will be recorded 30 seconds after cream removal
- J-Tip injection with 1% Xylocaine MPF or saline. Peak FLACC scale measurements and pulse ox measurements will be recorded within 5 seconds of injection (1st foot if bilateral)
- Following J-Tip injection there will be a 3-minute break, baby will be calmed during this time.
- Baseline #4: FLACC scale measurements and pulse ox measurements 3 minutes after J-Tip injection
- Tenotomy will be performed
  - FLACC Scale data and Pulse Ox data will be measured during the following events:
    - Percutaneous incision for TAL (1st foot if bilateral)- Peak FLACC scale and Pulse Ox data will be recorded within 5 seconds of poke of scalpel
    - Start of casting, after cast padding placed (1st cast if bilateral)

• End of casting (2nd cast if bilateral)

Adverse local effects of the cream and/or J-Tip injection will be noted (skin redness, swelling, rash, etc). Procedural complications will be recorded (excessive bleeding, concern for neurovascular injury, etc).

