#### **Reporting Adverse Events**

Any adverse event (clinical sign, symptom, or disease) temporally associated with the study treatment shall be documented in the adverse event (AE) CRF, except those events that are considered to be normal sequalae to the surgical procedure. All AE's meeting the above noted criteria are to be reported by the subject or observed by the Principal Investigator will be individually listed. The description of the event (confirmed diagnosis, if available), date of onset, date of resolution, action taken, severity and relationship to study treatment, and follow-up procedures will be reported.

The adverse event will be recorded in standard medical terminology. Additionally, the Principal Investigator will evaluate all adverse events as follows:

Action taken: whether or not the adverse event caused the subject to discontinue the study

Severity, to be assessed based on the table below:

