# Data Analysis

FLACC, heart rate, and oxygen saturation will be measured at 10 distinct time points (Table 1) during serial casting and following in-office TAL. Changes in FLACC score, heart rate, and oxygen saturation will be compared between treatment and control cohorts utilizing a two-way ANOVA with a Geisser-Greenhouse correction for matched time measures. A Sidak's multiple comparisons test will be utilized to assess differences between cohorts at each of the 10 time points assessed. To compare number of

complications between cohorts, data will be collected at 3-weeks post TAL and analyzed using a non-parametric Mann-Whitney test, given the ordinal nature of the data. Similar non-parametric analysis with correction for multiple comparisons between cohorts will be utilized to assess changes in responses to REDCap surveys. Statistical analysis will be conducted utilizing GraphPad Prism 8.3.0. Statistical significance will be p<0.05.

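### Sections 6, 8 and 10 do not agree on which local site reactions count for Aim 2, so some mild or tenotomy-day reactions may never reach the comparison

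*Combined protocol and SAP*

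**What the plan says.** Section 2.0 sets Aim 2 as: "Determine if there is a difference in the rate of adverse events between the two pain management methods". Its hypothesis is that the J-Tip injection "will not be associated with an increased rate of adverse events in comparison to L.M.X.4 cream". No margin is given.

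Four places govern which events are available for that comparison.

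- **Section 6.0, Tenotomy.** On the day: "Adverse local effects of the cream and/or J-Tip injection will be noted (skin redness, swelling, rash, etc"). A separate sentence covers the operation: "Procedural complications will be recorded (excessive bleeding, concern for neurovascular injury, etc"). Neither sets a severity or treatment threshold, and neither names a form.
- **Section 8.0, opening paragraph.** Some events may be regarded as normal consequences of the procedure, and these "will only be recorded if additional treatment is required or considered to be clinically significant". For detail the reader is told: "See specific indications for expected adverse events/complications due to nature of diagnosis". No such list follows.
- **Section 8.0, Reporting Adverse Events.** Events temporally associated with study treatment go on the adverse event form, "except those events that are considered to be normal sequalae to the surgical procedure". The exception for treated or clinically significant events is not repeated.
- **Section 10.0, Data Analysis.** To compare the number of complications, "data will be collected at 3-weeks post TAL", with a Mann-Whitney test. The source of the count is not named.

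**The concern.** The design is double-dummy. Every infant receives a cream, a jet injection and then an incision at the same heel-cord site. Section 7.0 lists the same local effects for both active products: rash, redness, irritation and swelling. After the incision, a blinded observer who sees mild redness or swelling has no stated basis for calling it a product reaction or a normal consequence of surgery. That judgement decides whether it reaches the adverse event form.

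The analysis text adds a second gap. Local reactions are noted on tenotomy day, but the comparison is described with data collected three weeks later. A cast goes on directly after the incision (Section 6.0), and Section 1.0 describes the post-tenotomy cast as staying on for 3 weeks. A transient reaction could be hidden and then gone by the visit.

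The Aim 2 hypothesis is one of no increase, tested at p<0.05 with no margin. Lost events make a non-significant result more likely, and that result would be read as support. An event that was never written down cannot be recovered at analysis.

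**Working it through.** The plan states no adverse event rate, margin or power for Aim 2, so there is no figure to reproduce. The check is a reading of the rules, followed by an illustration on assumed rates.

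**1. Following one mild, untreated episode of redness through the rules**

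| First seen | Section 6.0 note | Section 8.0 form | Section 10.0 comparison |
|---|---|---|---|
| After cream or J-Tip, before incision | Noted | Recorded: it cannot be a consequence of surgery that has not happened | Unclear: tenotomy-day records are not named as a source |
| After incision, same day | Noted if attributed to cream or J-Tip | Left off if judged a normal sequela | Unclear, for the same reason |
| At the 3-week visit | Not applicable | Depends on the same judgement | Included if recorded |

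Two points follow. The sequela judgement bites only on events first seen after the incision. The timing gap affects all tenotomy-day events. The two Section 8.0 statements also differ for a treated sequela: the opening paragraph records it and the later one does not say so.

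**2. Effect of equal loss in both arms**

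Let p1 and p2 be the true proportions of infants with a site reaction, and s the fraction kept, equal in both arms because assessors are blinded.

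- Recorded difference = s × (p1 − p2)
- Recorded risk ratio = (s × p1)/(s × p2) = p1/p2, unchanged

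Assumptions: 47 per arm (Section 10.0), two-sided 0.05, exact Fisher test on any reaction. The plan's test is Mann-Whitney on a count, so the powers show direction only.

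| Assumed true rates | Difference and power, all kept | Difference and power, half kept |
|---|---|---|
| 40% vs 15% | 25 points, 72% | 12.5 points, 30% |
| 40% vs 20% | 20 points, 49% | 10 points, 18% |
| 30% vs 10% | 20 points, 60% | 10 points, 22% |

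For 40% vs 15% with one third kept (13.3% vs 5%), the power is 15%. The risk ratios stay at 2.67, 2.0 and 3.0.

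**3. Effect of pooling everything into one outcome**

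Suppose surgical effects are counted too, with an independent background rate q equal in both arms. Then each arm's rate is 1 − (1 − p)(1 − q). For 40% vs 15% at 47 per arm:

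| q | Pooled rates | Power |
|---|---|---|
| 0 | 40% vs 15% | 72% |
| 20% | 1 − 0.60×0.80 = 52% vs 1 − 0.85×0.80 = 32% | 42% |
| 30% | 1 − 0.60×0.70 = 58% vs 1 − 0.85×0.70 = 40.5% | 32% |
| 50% | 1 − 0.60×0.50 = 70% vs 1 − 0.85×0.50 = 57.5% | 18% |

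Pooling therefore also costs power. Events should be recorded in full but tabulated apart.

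**The case against.** The strongest reply is that the plan already captures these events. Section 6.0 notes cream and J-Tip effects without a threshold and records procedural complications separately. Section 8.0 defines an adverse event regardless of causal relation, and its exemption is worded for the procedure, not for the study products. The order of steps also helps: cream removal, a new baseline, the injection and a 3-minute break all come before the incision, so reactions seen in that time are not surgical.

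Most of this stands. A reader might infer that Section 8.0 removes product redness and swelling from Aim 2 and so biases the result. The documents do not support that. The exemption does not name product effects, pre-incision reactions fall outside it, and removal would require the Aim 2 count to rest only on the adverse event form, which Section 10.0 does not say. Blinded, equal loss does not move the risk ratio.

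It is also fair to say that a 25-point gap is only assumed. Both arms receive a jet injection, so reactions to the jet itself are shared. Leaving surgical effects out of the outcome can protect the contrast, as step 3 shows.

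What the reply does not settle is attribution after the incision, the missing list of sequelae, and the missing link between tenotomy-day notes and the 3-week comparison. The Section 6.0 note itself depends on attributing the effect to the cream or J-Tip. The Schedule of Events includes an adverse event/complication review, but Section 10.0 does not tie it to the Aim 2 count.

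**Conclusion.** The concern holds as an inconsistency between Sections 6.0, 8.0 and 10.0, not as a demonstrated bias. Some mild site reactions first seen after the incision may be left off the adverse event form, and tenotomy-day reactions may be left out of the Aim 2 comparison. Either loss lowers the absolute difference and the power, in the direction that suits the hypothesis of no increase, while the risk ratio is unaffected if the loss is equal.

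The size cannot be estimated from the documents. The illustrated fall in power, from 49–72% to 18–30% when half of the events are lost, rests on assumed rates, an assumed retention fraction and a simpler test than the planned one. The conclusion does not depend on those figures. This is a cheap improvement to make while events can still be recorded.

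**What to change.** - **Section 8.0 and the adverse event form.** Record every reaction at the application or injection site in every infant, whatever its attribution. Note whether it was first seen before or after the incision. Make normal surgical sequela a tick-box completed blind, not a reason to omit. Bring the two Section 8.0 statements into line.
- **Section 10.0.** State that the Aim 2 comparison uses tenotomy-day records plus events up to the 3-week visit. Use one term throughout, since Section 2.0 speaks of adverse events and Section 10.0 of complications.
- **Reporting.** Tabulate local site reactions separately from procedural complications. Show results with and without events ticked as surgical sequelae, and do not pool all of them into one outcome.

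The cost is a few sentences, a timing field and a tick-box, with slightly more form-filling for mild events. While the cast covers the site, skin findings cannot be seen, so in practice the added records come from before casting and from the 3-week visit.

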#### **Definitions**

An AE can be any unfavorable and unintended sign, symptom, or disease temporally associated with the use of an investigational product, whether or not related to the investigational product.

#### **Reporting Adverse Events**

Any adverse event (clinical sign, symptom, or disease) temporally associated with the study treatment shall be documented in the adverse event (AE) CRF, except those events that are considered to be normal sequalae to the surgical procedure. All AE's meeting the above noted criteria are to be reported by the subject or observed by the Principal Investigator will be individually listed. The description of the event (confirmed diagnosis, if available), date of onset, date of resolution, action taken, severity and relationship to study treatment, and follow-up procedures will be reported.

The adverse event will be recorded in standard medical terminology. Additionally, the Principal Investigator will evaluate all adverse events as follows:

Action taken: whether or not the adverse event caused the subject to discontinue the study

Severity, to be assessed based on the table below:

# AE Severity Description

DEGREE Mild (Grade 1)	DESCRIPTION Symptom(s) barely noticeable to subject or does not make subject uncomfortable; does not influence performance or functioning; prescription drug not ordinarily needed for relief of symptom(s) but may be given because of the nature of subject.
Moderate (Grade 2)	Symptom(s) of a sufficient severity to make subject uncomfortable; performance of daily activity is influenced; subject is able to continue in study; treatment for symptom(s) may be needed.
Severe (Grade 3)	Cause severe discomfort; symptoms cause incapacitation or significant impact on subject's daily life; severity may cause cessation

# of study participation; treatment for symptom(s) may be given and/or subject hospitalized

Life Threatening Extreme limitation in activity, significant assistance required; (Grade 4) significant medical intervention/therapy required, hospitalization or hospice care required.

Relationship to treatment to be graded as:

RELATIONSHIP	DESCRIPTION				
	Any reaction that does not follow a reasonable temporal				
	sequence from administration of the study treatment AND that				
Not related	is likely to have been produced by the subject's clinical state or				
	other modes of therapy administered to the subject.				
	Any reaction that does not follow a reasonable temporal				
	sequence from administration of the study treatment or that is				
Unlikely	likely to have been produced by the subject's clinical state or				
	other modes of therapy administered to the subject.				
	A reaction that follows a reasonable temporal sequence from				
	administration of the study treatment OR that follows a known				
Likely	response pattern to the suspected treatment AND that could not				
	be reasonably explained by the known characteristics of the				
	subject's clinical state or other modes of therapy administered to				
	the subject.				
	A reaction that follows a reasonable temporal sequence from				
	administration of the study treatment AND that follows a known				
Definite	response pattern to the suspected treatment AND that recurs				
	with rechallenge, and/or is improved by changing treatment				

#### AE Relationship Description

# Serious Adverse Events (SAEs)

Events are classified as serious if they meet any of the following criteria (in accordance with 21 CFR 812.3(s)) and the recommendations of International Conference on Harmonization [Federal Register, October 7, 1997, Vol. 62, No. 194, pp 52239-45]):

- i. Any death.
- ii. Any life-threatening event, i.e., an event that places the subject, in the view of the investigator at immediate risk of death from the event as it occurred (does not include an event that, had it occurred in a more severe form, might have caused death).
- iii. Any event that requires or prolongs in-patient hospitalization.
- iv. Any event that results in persistent or significant disability/incapacity.
- v. Any congenital anomaly/birth defect diagnosed in a child of a subject who participated in this study following the study procedure.

- vi. Other medically important events that in the opinion of the investigator may jeopardize the subject or may require intervention to prevent one of the other outcomes listed in the definition above.
- vii. Any serious problem associated with the study treatment that relates to the rights, safety or welfare of study subjects.

The Principal Investigator or a member of the research staff will report all SAEs to the Institutional Review Board (IRB) according to the reporting requirements.

